**Continuing Review Form**

**1. Participant Enrollment**

- a. Number of participants entered (or number of specimens examined or charts reviewed) since the beginning of study. If this is a combined VA-Stanford study, in addition indicate how many of the participants (or number of VA specimens examined or VA charts reviewed) enrolled with a VA consent. If this is a multi-site study, in addition to the number of participants enrolled locally, include the number of participants enrolled study-wide.**

At the VA Palo Alto HCS, we have enrolled 122 participants since the beginning of the study on May 1, 2017. Of these, 70 were eligible for randomization to study treatment conditions.

At the collaborating site, the VA Syracuse, 234 participants have been enrolled since they began recruitment on February 1, 2017. Of these, 164 were eligible for randomization to study treatment conditions.

\*The original N for the entire study (i.e., across both sites) proposed for randomization to study conditions was 260. As is reflected in our DSMB report for 2019 (attached in Section 16) we reconsidered statistical power given that we had sufficient data to update assumptions we used to originally calculate power and the resultant sample size required to achieve it in the proposal. The original assumption of the standard deviation for the CAPS-5 (i.e., our primary outcome measure) was much higher (i.e., 16) than what we found in the data we had collected to date (i.e., SD = ~11). Therefore, we used this empirically-derived figure to recalculate power and the minimum required sample size needed to achieve it. Based on this, we needed to randomize at least 95 participants per condition instead of the originally proposed 130 per condition. We ultimately were able to randomize 114 to CS PTSD Coach and 118 to TAU, which will provide sufficient power to test our primary as well as our secondary outcomes.

- b. Number of: males, females, others or individuals whose sex/gender are unknown or not reported.**

Of the 122 enrolled at Palo Alto:  
Number of Females= 7  
Number of Males= 115

- c. Minority status of participants entered since beginning of study.**

29 African American/Black  
16 Asian/Pacific American  
5 Native American/Indian  
10 Hispanic  
17 Others  
(55 Caucasian/White)  
\*Categories not mutually exclusive

- d. Number of children (less than 18 years) entered since beginning of study.**

N/A

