2) Control Condition: PC-MHI Treatment as Usual (PC-MHI TAU): PC-MHI TAU consists of licensed independent providers providing brief assessment and interventions to Veterans and consultation to PACT staff.

The primary outcomes include: PTSD symptom severity (CAPS-5); specialty MH visits; and patient satisfaction with their treatment (CSQ, Patient Feedback Interviews).

Measures of potential mediation, moderation, breadth, and maintenance of treatment effects will include: PTSD Coach usage data; coping self-efficacy (CSE); depressive symptoms (PHQ-9); quality of life (WHOQOL-BREF); and for PTSD severity (PCL-5) across all time points.

Participants will be paid for time spent completing assessments at a rate of approximately \$20/ hour (baseline session- \$30, CAPS-5- \$20, post-treatment assessment- \$40, 16-week follow-up- \$20, 24-week follow-up- \$20, and \$20 bonus for completing all study procedures) and can earn up to \$150. Reimbursement will be by VA check mailed to their home. Participants will not be reimbursed for intervention sessions. Payments will be pro-rated to reflect percent completion.

**b) Explain how the above research procedures are the least risky that can be performed consistent with sound research design.**

The research procedures are the least risky that can be performed consistent with sound research design. The risks associated with participating are considered minimal but include the possibility of psychological discomfort associated with answering questions about traumatic events and psychological symptoms from them. To manage the possibility of this discomfort, study personnel who are licensed clinical psychologists (Drs. [name], [name], [name], and [name]) will be available. Risks of participating in Clinician-Supported PTSD Coach and PC-MHI TAU treatment conditions are minimized by having existing licensed mental health providers in VA primary care settings administer both conditions.

Although there is a risk that participation in this protocol will produce clinical-level psychological distress, research on the assessment of PTSD in both clinical and nonclinical populations indicates that this is an infrequent occurrence. In fact, patients report a desire to be asked about past experiences and psychological

**Title :** An RCT of a Primary Care-Based PTSD Intervention: Clinician-Supported PTSD Coach

**Approval Period:** Draft

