## Design and Methods Overview

This study is a two-site, two-arm, parallel RCT. Veterans with PTSD ( $N = 260$ ) will be recruited from VA PC clinics at Syracuse and Palo Alto. Participants will be randomized in equal proportions to receive 1) PC-MHI treatment as usual (PC-MHI TAU) or 2) CS PTSD Coach. Assessments will occur at baseline, 8 (post-treatment), 16, and 24 weeks post-baseline. Primary outcomes will be changes in PTSD severity and engagement in 2 sessions of specialty MH treatment. Thirty CS PTSD Coach participants will also complete a brief qualitative interview at post-treatment to evaluate their satisfaction with care. The study will use cutting-edge methodologies, including an innovative intervention package and objective app usage data to overcome limitations of self-report data.

**Data Collection Methodology.** The table below presents the measures that will be employed at each assessment time point. Baseline assessments will be conducted in person. Research staff will obtain informed consent and HIPAA authorization. Next self-report measures will be administered to assess inclusion criteria. Within one week of baseline (and prior to session 1 of CS PTSD Coach) participants will complete the CAPS-5 by phone with an independent assessor blind to condition. A post-treatment assessment (8 weeks) and two follow-up assessments (16 weeks and 24 weeks) will be conducted following baseline (Table 3). Follow-up assessments will be in person or by phone (based on participant preference) by local study staff, with the exception of the post-treatment CAPS-5, which will be conducted by phone by the independent assessor blind to condition. Several aspects of our assessment procedures, including options to assess by phone and brief assessment batteries, were designed to reduce participant burden and minimize drop-out.

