## Data Analysis and Statistical Considerations

**Power Analysis:** We propose randomizing 130 participants per condition (N = 260). Given this sample size, power was evaluated under a range of assumptions including a 15% loss to follow-up or 110 participants per condition (although under the ITT principle all 130 participants will be included in the analysis). Attrition in our pilot ([name], [name], Johnson et al., in press) at 8 weeks was 10%, similar to the 15% rate of a VA multi-site RCT with VA primary care patients. Attrition will be minimized by allowing intervention and follow-up sessions to be by phone and offering flexible scheduling of assessments (e.g., evening/ weekend times). The proposed sample size provides 80% power to detect a meaningful between group effect corresponding to a CAPS-5 difference of 7-15 points (or a Cohen's  $d$  of 0.4 or greater). These calculations conservatively assume a CAPS-5 SD ranging from 16-20 and a two-sided Wald test conducted with an alpha of .05. The effect size needed to detect a meaningful difference (i.e.,  $d = .4$ ) is smaller than what we found in our pilot work (i.e.,  $d = .55$ ). Equally important, this sample size provides adequate power to detect a statistical difference between conditions on percentages achieving clinically significant outcomes (i.e., can detect a 20% minimal difference, which is smaller than what our pilot data demonstrated, i.e., a 50% difference).

**Data Analysis:** The main goal of Aim 1 is to determine the effect of CS PTSD Coach on PTSD symptoms. More specifically, we will measure the impact of CS PTSD Coach on change in CAPS-5 score at 8 weeks. Mixed effects linear regression will be used to determine whether the effect of CS PTSD Coach on change in CAPS-5 score at 8 weeks is different from that of the comparison condition (i.e., PC-MHI TAU). As all participants will have a baseline score, they all will be included in the model, adhering to the ITT principle. The mixed effects model will include a subject-specific random effect to account for the correlation of CAPS-5 score within a person over time. Finally, because randomization is stratified by site, site will be included as a fixed effect in our model.

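### The protocol and SAP name different primary outcome sets and give no rule for which result decides the trial; with the two between-arm tests planned, the family-wise error could reach about 10%

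*Protocol*

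**What the plan says.** Three places describe the primary outcome differently.

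- **Protocol section 2(a), Study Procedures (three outcomes):** "The primary outcomes include: PTSD symptom severity (CAPS-5); specialty MH visits; and patient satisfaction with their treatment (CSQ, Patient Feedback Interviews". No number of visits is attached to the second outcome.
- **SAP, Design and Methods Overview (two outcomes):** "Primary outcomes will be changes in PTSD severity and engagement in 2 sessions of specialty MH treatment".
- **Protocol, Continuing Review Form item 1(a) (one measure):** the sample-size update refers to "the CAPS-5 (i.e., our primary outcome measure". The same item mentions secondary outcomes, but the SAP labels no outcome secondary.

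Alpha appears once, in the SAP Power Analysis for the CAPS-5: "a two-sided Wald test conducted with an alpha of .05". The SAP Data Analysis section plans a between-arm test of CAPS-5 change at 8 weeks (Aim 1) and of attending at least two specialty MH visits from week 1 to week 24 (Aim 2). No significance level is given for Aim 2. Aim 3 is a qualitative analysis of interviews with 30 CS PTSD Coach participants. The CSQ appears in the SAP only in the Table of Measures, at 8 weeks.

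**The concern.** A reader with both documents cannot tell which results decide whether the intervention worked. The aims are numbered, but nothing makes one test conditional on another, and nothing says whether one significant result is enough or all are needed. After the data are seen, either main outcome could be presented as the primary result.

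The choice could matter here. Protocol section 2(a) says CS PTSD Coach participants still at or above the PCL-5 threshold at session 4 will be recommended for specialty MH treatment. If the intervention reduces symptoms, fewer of its recipients would get that recommendation, so the two outcomes could point in different directions.

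There is also a gap that has nothing to do with multiplicity: the CSQ is a primary outcome in the protocol, yet no comparison between arms is specified for it.

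**Working it through.** **1. Outcomes side by side**

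| Outcome | Protocol 2(a) | SAP overview | Between-arm test in SAP |
|---|---|---|---|
| CAPS-5 / PTSD severity | Primary | Primary | Yes, 8 weeks (Aim 1) |
| Specialty MH care | Primary, no threshold | Primary, 2 sessions | Yes, at least 2 visits, weeks 1–24 (Aim 2) |
| Satisfaction (CSQ, interviews) | Primary | Not primary | None |

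The SAP therefore plans two between-arm tests of outcomes called primary.

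**2. The plan's own power figure**

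The SAP states: "The proposed sample size provides 80% power to detect a meaningful between group effect", with a Cohen's d "of 0.4 or greater". It randomises 130 per arm and assumes 15% loss; 130 × 0.85 = 110.5, so 110 per arm.

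- Noncentrality at d = 0.4: 0.4 × √(110/2) = 2.966.
- Power, two-sided .05: Φ(2.966 − 1.960) = 84.3% (84.0% by t test).
- Effect detectable with 80% power: (1.960 + 0.842) × √(2/110) = 0.378.

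The stated 80% is not matched exactly, but 0.378 rounds to 0.4, so the difference looks like rounding on the conservative side. It does not affect this point. The calculation is for the CAPS-5 alone at the full .05.

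**3. Family-wise error**

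Assumptions not in the documents: each test is run at .05, and success is claimed if any one is significant.

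- One primary outcome: 5%.
- Two independent tests: 1 − 0.95² = 9.75%.
- Two correlated test statistics (bivariate normal, assumed correlations): 9.5% at r = 0.3, 9.1% at r = 0.5, 8.4% at r = 0.7. Because the tests are two-sided, a negative correlation of the same size gives the same figure.
- False positives favouring CS PTSD Coach only, two independent tests: 1 − 0.975² = 4.9%.

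**4. What error control costs the CAPS-5 test**

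The Continuing Review Form reports 114 and 118 randomised. With the SAP's 15% attrition, 114 × 0.85 = 96.9 and 118 × 0.85 = 100.3, so about 97 and 100. The noncentrality at d = 0.4 is 0.4 × √(97 × 100/197) = 2.807.

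| t-test power at d = 0.4 | alpha .05 | alpha .025 |
|---|---|---|
| 97/100 (15% attrition) | 79.8% | 70.8% |
| 114/118 (no attrition) | 85.8% | 78.5% |

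A fixed sequence that tests the CAPS-5 first keeps the .05 column. An equal split over two outcomes moves it to the .025 column, a loss of 9 points with attrition (79.8 − 70.8).

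**The case against.** **The contradiction may be narrower than three versions.** The Continuing Review Form is a status report, and its wording identifies the CAPS-5 while explaining an updated SD. It does not define the outcome set. This is fair: the firm conflict is three outcomes in the protocol against two in the SAP, and it turns largely on whether satisfaction is primary.

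**Separate aims need no joint adjustment.** Aims 1 and 2 ask different questions with different models, and the documents define no single trial-level claim. Statisticians differ on this, and it is why the error rate can only be given conditionally. The defence works only if the plan says the aims will be claimed separately, and it does not.

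**Both outcomes were intended to matter.** Protocol section 1(b) names symptom reduction and greater use of mental health care together, and section 2(g) refers to primary aims in the plural. Placing attendance behind the CAPS-5 is therefore a choice for the sponsor.

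**The rule may be elsewhere.** The grant protocol is listed as an attachment but is not in the supplied text, and it may state an order. If so, the SAP should carry it.

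**A stronger reading is tempting.** A reader might infer that the false-positive rate is 10% to 14%. Three independent tests would give 1 − 0.95³ = 14.3%, but that needs a third confirmatory comparison, and the SAP plans none for satisfaction. Even the 10% end is an upper figure that depends on independence, on an any-one-significant rule and on .05 for Aim 2, where no level is stated.

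**Conclusion.** The inconsistency stands. The two documents name different primary sets, the supplied text contains no order, alpha split or success rule, and a protocol primary outcome (the CSQ) has no between-arm analysis.

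The effect on error is bounded. It is 5% if the CAPS-5 alone is primary. It could reach about 10% if both planned tests are run at .05 and either counts as success: 9.75% under independence, about 9.1% at an assumed correlation of 0.5. The documents do not show that the trial's error rate is 10% or more, because they fix neither the success rule nor the correlation. The need to reconcile the outcome sets and specify a CSQ comparison does not depend on these figures.

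**What to change.** Issue a dated clarification of both documents before outcomes are compared by arm. The Continuing Review Form reports enrolment and interventions complete, data still being prepared and no interim findings, so this appears possible. The date matters because data collection is over; the clarification should state who had seen outcome data by arm when it was signed.

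1. **Use the same primary set in both documents**, with the specialty MH outcome defined as at least two visits by 24 weeks.
2. **State one error-control rule.** The natural option is a fixed sequence: 8-week CAPS-5 change at two-sided .05, then specialty MH attendance at .05 only if the CAPS-5 result is significant. Both power calculations rest on the CAPS-5, and its power is unchanged (about 80% at d = 0.4 with 15% attrition). If the sponsor keeps both outcomes as co-primary, with either able to establish success, name an alpha-sharing procedure such as Holm or Hochberg. CAPS-5 power would then lie between about 71% and 80%, depending on the attendance result.
3. **List the CSQ as secondary** and compare it between arms at 8 weeks by linear regression on condition and site. Keep the interviews as the descriptive analysis already planned.

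The work is a short amendment to the text and one added regression; no new data are needed. The real cost is that, under the fixed sequence, a specialty MH result is not confirmatory if the CAPS-5 result is not significant.

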### 3. Background

- a) Describe past experimental and/or clinical findings leading to the formulation of the study.**

We conducted a pilot study that investigated the feasibility and

**Title :** An RCT of a Primary Care-Based PTSD Intervention: Clinician-Supported PTSD Coach  
**Approval Period:** Draft

preliminary efficacy of Clinician- Supported PTSD Coach (CS-PTSD Coach), using recruitment and procedures similar to those of the current study ([name], [name], et al., in press - attached). Twenty PC patients with significant PTSD symptoms (PCL  $\geq$ 40) were enrolled over 2 months and randomized to CS-PTSD Coach or Self-Managed (SM) PTSD Coach, which consisted of one 10-minute session to provide instructions on how to use PTSD Coach. PC-MHI providers delivered CS and SM PTSD Coach. Participants were 95% male, 65% White with an average age of 42 (SD=12). Nearly half (45%) were employed, 15% were students, and 35% were retired. Previous deployments were 50% OEF, 40% OIF/OND, 15% Gulf War I, 5% Vietnam. Ninety percent owned their own smart device. Retention was 100% in the treatment sessions and 90% (18/20) at the post-treatment assessment. Both treatments resulted in reductions in PTSD symptoms, with 7 Clinician-Supported PTSD Coach and 3 Self-Managed PTSD Coach participants reporting clinically significant improvements. Clinician-Supported PTSD Coach resulted in more specialty PTSD care use post-intervention and possibly greater reductions in PTSD symptoms.

**b) Describe any animal experimentation and findings leading to the formulation of the study.**

NA

**4. Radioisotopes or Radiation Machines**

**a) List all standard of care procedures using ionizing radiation (radiation dose received by a subject that is considered part of their normal medical care). List all research procedures using ionizing radiation (procedures performed due to participation in this study that is not considered part of their normal medical care). List each potential procedure in the sequence that it would normally occur during the entire study. More Info**

Identify Week/Month of study	Name of Exam	Identify if SOC or Research
------------------------------	--------------	-----------------------------

**b) For research radioisotope projects, provide the following radiation-related information:**

**Identify the radionuclide(s) and chemical form(s).**

**For the typical subject, provide the total number of times the radioisotope and activity will be administered (mCi) and the route of administration.**

**If not FDA approved provide dosimetry information and reference the source documents (package insert, MIRD calculation, peer reviewed literature).**

**c) For research radiation machine projects, provide the following diagnostic procedures:**

**For well-established radiographic procedures describe the exam.**

**For the typical subject, identify the total number of times each will be performed on a single research subject.**

**For each radiographic procedure, provide the setup and technique sufficient to permit research subject dose modeling. The chief technologist can usually provide this information.**

**For radiographic procedures not well-established, provide FDA status of the machine, and information sufficient to permit research subject dose modeling.**

**d) For research radiation machine projects, provide the following therapeutic procedures:**

**Title :** An RCT of a Primary Care-Based PTSD Intervention: Clinician-Supported PTSD Coach  
**Approval Period:** Draft

**For a well-established therapeutic procedure, identify the area treated, dose per fraction and number of fractions. State whether the therapeutic procedure is being performed as a normal part of clinical management for the research participants's medical condition or whether it is being performed because the research participant is participating in this project.**

**For a therapeutic procedure that is not well-established, provide FDA status of the machine, basis for dosimetry, area treated, dose per fraction and number of fractions.**

**5. Devices**

a) Please list in the table below all Investigational Devices (including Commercial Devices used off-label) to be used on participants.

**5.1 Device Name : PTSD Coach**

Describe the device to be used.

**PTSD Coach is a VA mobile app that is freely available (since 2011)to the public in both the Apple App Store and Android Google Play market. It is designed to help those with PTSD symptoms self-manage their distress using information, access to support resources, CBT-based symptom coping tools, and self-assessment and monitoring of symptoms.**

**Manufacturer :** VA

**Risk :** Non-significant

Y I confirm the above are true.

**Rationale for the device being non-significant risk:**

The PTSD Coach is a publically available mobile app that provides sound psycho-educational information about PTSD and its treatment as well as cognitive-behavioral tools to help individuals with PTSD cope with acute distress. These tools include anxiety reduction skills such as deep breathing, positive imagery, and progressive muscle relaxation. It also includes coping self-statements intended to help individuals cope with difficult situations and emotional states. PTSD Coach does not include any trauma-focused interventions (e.g., prolonged exposure).

**Sponsor of Project**

**Indicate who is responsible for submitting safety reports to the FDA:**

Y The sponsor is the STANFORD (SU, SHC, LPCH, VA) investigator.

**Please read the following:**

Sponsor-Investigator Research Requirements

**If you would like further information on this process and/or assistance prior to submitting your protocol contact: The Stanford Center for Clinical and Translational Education and Research (Spectrum) at [[contact]](mailto:[contact]) or for cancer research contact: [[contact]](mailto:[contact])**

Y I have read and understand the above guidance.

**Ordering, Storage and Control**

**To prevent the device being used by a person other than the investigator, and in someone other than a research participant: Confirm that the device will be handled according to the SHC/LPCH policy for Investigational New Devices or as appropriate. If no, please provide an explanation. :**

Y Confirm?

\_\_\_\_\_

**Title :** An RCT of a Primary Care-Based PTSD Intervention: Clinician-Supported PTSD Coach

**Approval Period:** Draft

**b) Please list in the table below all IDE Exempt Devices (Commercial Device used according to label, Investigational In Vitro Device or Assay, or Consumer Preference/Modifications/Combinations of Approved Devices) to be used on participants.**

